Building Mobile HIV Prevention and Mental Health Support in Low-resource Settings

NCT06229132 2/15/2025

BACKGROUND

In July 2021, the study team received a supplement to the R01 grant to enroll a small sample (N=45) of transgender and gender-diverse (TGD) Romanians in addition to the original sample of 800 GBM. This decision is based on the following rationale. TGD individuals remain a hidden group in the Central Eastern European (CEE) country of Romania, with few protections, few equal rights, and many unmet needs. Emerging research with TGD persons in the region indicates that TGD Romanians report particularly high rates of depression, HIV, and hazardous alcohol use, primarily driven by the country's high structural stigma. Romania's healthcare system has little expertise for addressing these syndemic health threats. No targeted needs assessments or interventions exist to date in order to remedy these adversities and promote the wellbeing of TGD in Romania, or anywhere in CEE – the region with the fastest-growing HIV epidemic in the world. In response, we proposed to create and pilot-test the first intervention in CEE to address the mental, sexual, and behavioral health of TGD people. Compared to the GBM sample, however, TGD participants in formative work indicated that a mental health focus, rather than a sexual or behavioral health focus (while still addressing these as relevant to each participant) should be adopted. As a result, our EQuIP (Empowering Queer Identities in Psychotherapy) intervention is being delivered in this supplement to the TGD sample of 25 participants.

In Aim 1, we will identify unique needs of TGD Romanians via focus groups. Findings will be used in Aim 2 to modify the intervention manual to address gender minority stress and other TGD-specific determinants of mental health, hazardous alcohol use, and HIV risk. In Aim 3, we will evaluate the adapted intervention's feasibility, acceptability, and efficacy potential in a one-arm trial with 25 TGD Romanians.

Research Aims & Abstracts

The aim of this study is to evaluate the intervention's feasibility, acceptability and efficacy potential in a one-arm trial with 25 TGD Romanians. Participants will receive 16 weekly mHealth sessions hypothesized to reduce depression, anxiety, HIV risk, and hazardous alcohol use; outcome data will be collected at baseline and 5-month follow-up.

Scientific Abstract

Transgender and gender diverse (e.g., gender non-binary) (TGD) individuals remain a hidden group in the Central Eastern European (CEE) country of Romania, with few protections, few equal rights, and many unmet needs. Emerging research with TGD persons in the region indicates that TGD Romanians report particularly high rates of depression, anxiety, HIV, and hazardous alcohol use, primarily driven by the country's high structural stigma. Romania's healthcare system has little expertise for addressing these syndemic health threats. No targeted needs assessments or interventions exist to date in order to remedy these adversities and promote the wellbeing of TGD in Romania, or anywhere in CEE – the region with the fastest-growing HIV epidemic in the world. In response, we propose to create and pilot-test the first intervention in CEE to address the mental, sexual, and behavioral health of TGD people. EQuIP, MPI [name]'s intervention, was tested with various populations in the US and in China. The first pilot study tested successfully the efficacy of a minority-stress-focused cognitive—behavioral therapy (CBT) intended to improve mental and behavioral health for sexual minority women. This treatment was adapted for the present research based on local Romanian TGD needs uncovered in the first part of this pilot study (which ended in 2021). The adaptation was guided by the gender minority stress framework that acknowledges unique TGD stressors, whose impact the intervention intends to modify. As such, the intervention consists of 16 1-hour sessions delivered by trained therapists on Zoom. The team will evaluate the new intervention's feasibility and acceptability in a one-arm trial with 25 TGD Romanians. Data will be collected at baseline and 5-month follow-up.

STUDY DESIGN

For the transgender sample, the study team completed focus groups with 19 TGD, 6 providers and stakeholders to identify the most suitable intervention targets and approach. This process led the team to identify social gender affirmation, and accompanying mental health issues, as primary intervention targets for TGD Romanians, who face frequent minority stress as a function of difficulties finding providers and hormonal treatment, school and employment discrimination, and lack of affirming providers. Given the role of minority stress in TGD Romanian's lives, the team has adapted the EQuIP LGBTQ-affirmative CBT intervention ([name] et al., 2022) for this study. The team will evaluate the intervention's feasibility,

acceptability and efficacy potential in a one-arm trial with Romanian TGD individuals who report depression or anxiety. Participants will receive 16 weekly mHealth sessions delivered on the HIPAA-compliant Zoom platform, and hypothesized to address the outcomes of interest; data will be collected at baseline and 5-month follow-up.

Eligibility. Potential participants will be eligible if they 1) identify on the transfeminine, transmasculine, or gender non-binary spectrum and declare a gender that is different from their assigned birth sex; 2) be 18 years old; 3) report depression or anxiety symptoms (score past 90-day symptoms of depression or anxiety: 2.5 or higher score on depression or anxiety subscale of the Brief Symptom Inventory); 4) own a phone, tablet, or laptop. Additionally, to be eligible, participants must not be receiving regular mental health services on an ongoing basis (e.g., more than once per month) and cannot have received 8 or more sessions of CBT within the past 12 months.

Intervention Content. MPI [name] (Yale University) has created and tested EQuIP with various populations in the US and in China. The first pilot study tested the efficacy of a minoritystress-focused cognitive—behavioral therapy (CBT) intended to improve mental and behavioral health for sexual minority women. The intervention was delivered to young adult sexual minority women in the US (n = 60; M age = 25.58; 41.67% racial/ethnic minority; 43.33% transgender/nonbinary) experiencing depression/anxiety and past 90-day heavy alcohol use. Compared to waitlist (n = 30), participants randomized to immediately receive EQuIP (n = 30)experienced significantly reduced depression and anxiety (d = 0.85, 0.86, respectively). In pre to post-intervention pooled analyses, effect sizes for minority stress processes (mean d =.25) and universal risk factors (mean d = .48) were reduced. This treatment was adapted for the present research based on local Romanian TGD needs uncovered in the first part of this pilot study (which ended in 2021). As such, the intervention will consist of 16 1-hour sessions delivered by our trained therapists on Zoom. These sessions are based on 6 principles of LGBTQ-affirming CBT, as follows: (1) normalizing mood and anxiety as a common response to LGBTQ related stress; (2) challenging persistent, inflexible LGBQ-related stress-induced cognitions; (3) encouraging assertive behavior and open self-expression to effectively cope with the consequences of LGBTQrelated stress; (4) validating LGBTQ clients' unique strengths; (5) building authentic relationships as an essential resource for LGBTQ people's mental health; and (6) recognizing intersectional identities as a source of stress and resilience.

STATISTICAL ANALYSIS

Feasibility and acceptability measures and analyses. Feasibility will be assessed by: 1) examining screener data for eligibility ratio and reasons for enrollment refusal; and 2) participants' rating of participation ease, including in using the mobile platform, and counselors' rating of intervention delivery ease (mean score of ³4 on a scale of 1-5 indicates high feasibility). Acceptability will be assessed by: 1) tracking # of sessions completed, with a minimum session completion dose by ³80% of participants (which is ³10 sessions, completed by 86% of participants); and 2) post-intervention ratings (mean score of ³4 on a scale of 1-5 indicates high acceptability) of the: a) usefulness of intervention content and perception of personal progress, b) intervention structure, c) delivery modality, d) counselor expertise, and e) therapeutic alliance including trust and comfort. Finally, exit interviews with all participants and counselors will qualitatively assess intervention accessibility and participation comfort, content relevance and TGD-sensitivity, perceived impact on health and wellbeing, duration, and if participants would recommend it to friends (compensated with the Romanian equivalent of \$30).

Intervention outcomes. This pilot will establish effect sizes necessary to power a future larger trial for our main outcomes: depression, anxiety, HIV risk, and hazardous alcohol use.

Analyses for intervention evaluation. Findings will allow us to assess the intervention's potential impact on mental health, HIV risk, hazardous drinking, and psychosocial mechanisms theorized to underlie the adverse impact of gender minority stressors on participants' health. Outcome distributional properties will be examined using standard summary statistics (means, SDs, medians, skew, kurtosis) and graphical summaries (boxplots, density plots). For continuous or discrete variables with skewed distributions (e.g., hazardous drinking frequency), we will investigate transformation to symmetry (e.g., log and square root). Given the small sample size (n = 25), we will not have sufficient power to use traditional statistical significance testing. However, in order to gather preliminary data on the magnitude of the intervention's possible impact on each outcome, we will conduct paired-sample t-tests to assess pre-post intervention change (from baseline to immediately post-intervention 5 months later).

Power. Utilizing the t-tests results, we will calculate Cohen's d as a measure of effect size and interpret effects as small (d = 0.2), medium (d = 0.5), and large (d = 0.8) following published guidelines.

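### Does the 86% in the session-completion sentence create a second acceptability threshold alongside the 80%?

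*Combined protocol and SAP*

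**What the plan says.** Under Statistical Analysis, the paragraph on feasibility and acceptability measures assesses acceptability in two quantitative ways. The first tracks the number of sessions completed and asks for a "minimum session completion dose by ³80% of participants (which is ³10 sessions, completed by 86% of participants", where the parenthesis explains the dose. The second is a set of post-intervention ratings in five areas, where a mean of at least 4 on a 1-to-5 scale indicates high acceptability. Exit interviews add a qualitative assessment.

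The sample size is 25. It is given in the Background, which describes evaluating feasibility, "acceptability, and efficacy potential in a one-arm trial with 25 TGD Romanians", and again in the paragraph on analyses for intervention evaluation: "Given the small sample size (n = 25". The 86% appears nowhere else in the document. The text does not say whether it is a target, an expected rate or a result from some other group.

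**The concern.** A prospective criterion should have one number. This sentence has two for the same event, and the second has no source. If the 86% were a rival cut-off, 20 or 21 completers would count as acceptable on one reading and not on the other, and the choice could be made after the data were seen. Acceptability is a stated aim of the trial, and the plan says it lacks power for conventional significance testing, so the benchmarks carry much of the interpretation. This is also the only numeric benchmark based on session completion. The 86% looks odd as well, because no whole number of completers out of 25 gives it.

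**Working it through.** **Inputs.** Sample size n = 25, the 80% figure and the 86% figure, all from the Statistical Analysis section. The earlier pilot under Intervention Content had 30 per arm ("Compared to waitlist (n = 30), participants randomized to immediately receive EQuIP (n = 30"), 60 in all. The plan gives no count of completers, so there is no derived figure of its own to reproduce. It gives no expected completion rate either, so the true rates below are assumptions.

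**Step 1: what each figure would require.** Completers needed = p × n, rounded up.
- 80%: 0.80 × 25 = 20, so 20.
- 86%: 0.86 × 25 = 21.5, so 22 (22/25 = 88%).

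Two cut-offs would disagree only at 20 completers (80%) or 21 (84%).

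**Step 2: how often that would happen, if 86% were a cut-off.** With X binomial(25, p), the chance of disagreement is P(X ≥ 20) − P(X ≥ 22). The last column is taken before rounding.

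| Assumed true rate | P(X ≥ 20) | P(X ≥ 22) | P(20 or 21) |
|---|---|---|---|
| 75% | 0.378 | 0.096 | 0.282 |
| 80% | 0.617 | 0.234 | 0.383 |
| 85% | 0.838 | 0.471 | 0.367 |
| 86% | 0.873 | 0.529 | 0.345 |
| 90% | 0.967 | 0.764 | 0.203 |

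So the disagreement would be common, roughly 20% to 38% over this range, but only on that reading.

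**Step 3: is 86% a cut-off?** The ≥ sign survives text extraction, as ³, in four places in this paragraph: the feasibility rating of 4, the 80%, the 10 sessions and the acceptability rating of 4. It is absent from the 86%. A sign lost at that one place is unlikely. The grammar agrees: the 80% is written as a requirement, while the 86% follows a past participle inside a parenthesis whose job is to say what the minimum dose is.

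**Step 4: could 86% be a result from a group the plan names?**
- This sample of 25: 21/25 = 84% and 22/25 = 88%, so no.
- The earlier pilot: 26/30 = 86.7% and 52/60 = 86.7%, which round to 87%, so not from the full groups.
- Ratios such as 18/21, 19/22, 24/28 and 25/29 do round to 86%.

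The source cannot be identified from the document. A percentage that no count out of 25 can produce would also be a strange threshold to choose for 25 people.

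**Step 5: the verdict as written.** With at least 80% as the criterion, 20/25 = 80% passes and 21/25 = 84% passes. No result is judged in two ways.

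**The case for a change.** The best case for acting is that reading the 86% as a supporting figure does not tidy the sentence. A result of unknown origin still sits inside a prospective criterion, and the plan says only participants, without stating whether that means everyone enrolled or only those who started treatment. The denominator can matter. As an illustration, 19 completers among 22 who started is 19/22 = 86% and passes, while the same 19 among 25 enrolled is 19/25 = 76% and fails. Rewriting the sentence would cost almost nothing.

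The missing source and the unstated denominator are real gaps. They do not make the plan produce a wrong result. In a one-arm pilot of 25, an analyst would take all enrolled participants as the denominator, and reporting the counts lets a reader recompute any other version.

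Writing the rule as a fixed count of 20 would bring its own problem if enrolment missed 25. With 26 enrolled, 80% needs 21 (0.80 × 26 = 20.8), and 20/26 is only 77%; with 23 enrolled, 80% needs 19 (0.80 × 23 = 18.4). The proportion in the plan adapts to the number enrolled.

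Precision can also be raised: 20/25 has an exact 95% interval of 59% to 93%, and a true rate of 70% would still reach 20 of 25 with probability 0.193. Both figures are right, but they describe any benchmark in 25 people and would be the same if the 86% were deleted. An interval alongside the proportion is a reasonable reporting habit; its absence from the criterion is not a fault in the criterion.

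**Conclusion.** The concern does not hold as a reason to change the plan. The criterion as written is at least 80% of participants reaching the minimum number of sessions, which is 20 of 25 at the planned size. The 86% is an unattributed descriptive figure, a clerical untidiness. The disagreement probability of 38% at a true rate of 80% arises only if the 86% is taken as a second cut-off, a reading that the placement of the ≥ signs and the grammar make unlikely.

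The consequence is limited even then. Session completion is one part of the acceptability assessment, alongside ratings in five areas and exit interviews, and no error rate or progression decision depends on it. The unstated denominator is a detail that analysts would fill sensibly.

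This conclusion rests on the ≥ signs having been extracted faithfully and on all enrolled participants being the denominator. It takes no position on the 10-session minimum, which is a clinical matter.

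### The pilot promises effect sizes to power a later trial, but the only one planned is an uncontrolled pre-post d in 25 people

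*Combined protocol and SAP*

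**What the plan says.** The Background describes Aim 3 as an evaluation of feasibility, "acceptability, and efficacy potential in a one-arm trial with 25 TGD Romanians". Under Research Aims & Abstracts there are two time points: "outcome data will be collected at baseline and 5-month follow-up". No passage describes a comparator, an external benchmark or an adjustment for untreated change.

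Under Statistical Analysis, the Intervention outcomes paragraph states: "This pilot will establish effect sizes necessary to power a future larger trial for our main outcomes". It applies this to all four main outcomes and does not describe the future trial's design.

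The next paragraph, on analyses for intervention evaluation, plans summary statistics including means and SDs. It concedes too little power for significance testing. To gauge the intervention's "possible impact on each outcome, we will conduct paired-sample t-tests to assess pre-post intervention change".

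The Power paragraph then says: "Utilizing the t-tests results, we will calculate Cohen's d as a measure of effect size", with benchmarks of 0.2, 0.5 and 0.8. It names no standardising SD and plans no confidence interval for d.

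The Eligibility paragraph requires symptoms at entry: "2.5 or higher score on depression or anxiety subscale of the Brief Symptom Inventory".

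**The concern.** A pre-post d measures how far scores moved in treated people. A controlled trial is powered on the difference between treated and untreated movement. With one arm and two time points, nothing in the plan separates the treatment effect from natural course, other events over five months, or the effect of repeated assessment.

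Depression and anxiety carry a further risk because people enter on a high score on one of those subscales. Some later fall could then be regression to the mean. For HIV risk and drinking, even the direction of background change is unknown.

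The purpose sentence has no such limit. If the pilot d were carried into a sample-size formula as a between-arm effect, the later trial could be too small or too large.

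**Working it through.** **Inputs from the documents:** one arm, n = 25, paired t-tests, Cohen's d with 0.5 labelled medium. The plan gives no derived figure to reproduce: n = 25 has no stated derivation, and the Power paragraph contains no power calculation.

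**Assumptions (mine):** a future two-arm parallel trial with 1:1 allocation, two-sided alpha 0.05 and 80% power; an observed d of 0.5; equal pre and post SDs; and a range for background change and for the pre-post correlation r. The documents give none of these except the 0.5 benchmark.

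**Step 1, precision.** Let d_z be mean change divided by the SD of change. Then t = d_z × √n = 0.5 × 5 = 2.5 on 24 degrees of freedom. Inverting the noncentral t distribution gives noncentrality limits of about 0.39 and 4.56. Dividing by 5 gives a 95% CI for d_z of 0.08 to 0.91. Even without bias, the interval runs from almost nothing to beyond the plan's large benchmark of 0.8.

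**Step 2, per-arm size if 0.5 is read as a between-arm effect.** The normal approximation is n = 2(1.960 + 0.842)²/d² = 15.70/d² = 15.70/0.25 = 62.8. The noncentral t calculation gives 63.8, so 64 per arm.

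**Step 3, remove background change.** The net effect is 0.5 minus background change. Take r = 0.5 first, where d_z equals d in raw SD units:

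| Background part of 0.5 | Net d | Power at 64 per arm | Needed per arm |
|---|---|---|---|
| 0 | 0.5 | 80% | 64 |
| 0.1 | 0.4 | 61% | 100 |
| 0.2 | 0.3 | 39% | 176 |

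If untreated people would have worsened by 0.1, the net effect is 0.6. Power at 64 per arm is then 92%, and 45 per arm would be enough. The error can go either way.

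**Step 4, dependence on r.** With equal pre and post SDs, d in raw SD units = d_z × √(2(1 − r)). The conversion factors are 1.183 (r = 0.3), 1.000 (0.5), 0.894 (0.6) and 0.632 (0.8). A d_z of 0.5 is therefore 0.59, 0.50, 0.45 or 0.32 raw SDs. Repeating the noncentral t calculation on the converted values gives the number needed per arm:

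| Net d_z | r = 0.3 | r = 0.5 | r = 0.6 | r = 0.8 |
|---|---|---|---|---|
| 0.5 | 46 | 64 | 80 | 158 |
| 0.4 | 72 | 100 | 124 | 247 |
| 0.3 | 126 | 176 | 219 | 438 |

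The step 3 figures therefore hold for d_z only at r = 0.5. Without the named SD and r, a reader cannot convert the pilot's d.

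**Step 5, regression to the mean.** Its size depends on three things the documents do not give: whether the screening score doubles as baseline, where 2.5 lies in SD units of the screened population, and how symptoms correlate over time. If baseline is re-measured and symptoms behave as a stable trait plus independent error, it is about zero. If the screening score is the baseline, it need not be small. I put no figure on it.

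**The case against.** The best defence is that this is a pilot and the plan largely says so. Aim 3 speaks of efficacy potential. The analysis paragraph presents its results as preliminary, refers to possible impact, concedes low power and calls the comparison pre-post. The planned means and SDs are proper inputs for a later trial. All of that stands, and a one-arm pilot is a reasonable choice. But these cautions govern the analysis paragraph. They do not withdraw the separate statement that the pilot will supply what is needed to power a larger trial.

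A second defence also stands in part. The documents never say that the pilot d will be entered as a between-arm effect, nor that the future trial will be controlled. The per-arm figures therefore illustrate a natural use of the sentence, not a stated plan.

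A reader might infer three stronger points that the documents do not support:

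- *That d is certainly inflated by regression to the mean.* It may be, but the documents leave open whether the amount is nil or substantial.
- *That the plan confuses controlled and uncontrolled effect sizes.* The Intervention Content paragraph labels both kinds. It ties one set to a waitlist comparison and introduces the other with "In pre to post-intervention pooled analyses, effect sizes for minority stress processes". Both are background results, and nothing combines them with the pilot's d.
- *That the unnamed SD is an error in itself.* It is missing detail. Deriving d from the t-test results points towards d_z, though it does not settle the matter.

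**Conclusion.** The point holds as a correction to one purpose statement. The planned d is uncontrolled and, at n = 25, imprecise (0.08 to 0.91 around an observed d_z of 0.5). It cannot on its own be the planning effect for a controlled trial in any of the four outcomes.

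The cost of using it that way depends on assumptions. With a two-arm trial, two-sided 0.05, 80% power and r = 0.5, a trial of 64 per arm would have 61% or 39% power if 0.1 or 0.2 of the observed 0.5 were background change. Other correlations change those figures, and opposite background change reverses the direction.

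This should be fixed, but it is a matter of wording and reporting. The one-arm design, the feasibility and acceptability aims, the participants and the procedures are not in question.

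**What to change.** Replace the sentence in the Intervention outcomes paragraph with:

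> This pilot will estimate, with 95% CIs, within-person change, outcome SDs, the baseline to 5-month correlation and retention. Because there is no control group, the pre-post d describes change only and will not on its own be used as the planning effect for a future controlled trial.

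In the Power paragraph, report d with its 95% CI and name its SD. One option is d_z from the SD of change, given alongside the pre-post correlation so that readers can convert it.

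This needs no extra participants, visits or procedures. The cost is a more modest stated deliverable and a little more reporting.

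### Does the lack of a named measure, recall period or scoring for the four main outcomes leave the pilot's effect sizes unusable?

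*Combined protocol and SAP*

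**What the plan says.** In the combined protocol and SAP, the Intervention outcomes paragraph says the pilot will establish "effect sizes necessary to power a future larger trial for our main outcomes: depression, anxiety, HIV risk, and hazardous alcohol use". These are constructs; no scale is attached to any of them.

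Under Eligibility, a symptom scale is named for entry only: "score past 90-day symptoms of depression or anxiety: 2.5 or higher score on depression or anxiety subscale of the Brief Symptom Inventory". Nothing says whether it is repeated as an outcome. Under Intervention Content, a 90-day window appears once more, describing participants in an earlier US study as "experiencing depression/anxiety and past 90-day heavy alcohol use".

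The Analyses paragraph specifies paired t-tests at n = 25, mentions drinking frequency as an example of a skewed variable that might be transformed, and disclaims adequate power for significance testing. The Power paragraph turns the t-test results into Cohen's d, with benchmarks of 0.2, 0.5 and 0.8.

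On timing, Research Aims & Abstracts says "outcome data will be collected at baseline and 5-month follow-up", while the Analyses paragraph describes the comparison as "from baseline to immediately post-intervention 5 months later".

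**The concern.** A standardised effect has meaning only for a stated variable. If the variable is open, so are the weeks it covers, its SD and the reading of the small, medium and large labels. Recall period and response format are set when the questionnaire is given and cannot be recovered later. If two alcohol or HIV-risk measures were collected, the plan does not say which supplies the main d.

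The same document gives its feasibility and acceptability ratings a 1-5 scale and a threshold of 4, which makes the silence on the health outcomes stand out. Timing adds to it: with a long recall period, the follow-up answers could cover weeks when participants were still in treatment and so understate the change.

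At stake is the pilot's stated use, which is to size a later trial.

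**Working it through.** The documents give no alpha, power, SD or target effect, so there is no figure of the plan's to reproduce. Everything below except the text check rests on assumptions.

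**1. What the text gives for each outcome**

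| Outcome | Given as an outcome | Given elsewhere |
|---|---|---|
| Depression | nothing | inventory subscale, 90 days, cut-off 2.5 (entry) |
| Anxiety | nothing | the same (entry) |
| HIV risk | nothing | nothing |
| Alcohol | drinking frequency, as an example of skew | 90-day heavy use (earlier US study) |

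The factual premise is correct.

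**2. What a 90-day recall would contain**

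Take 5 months as 152 days, so a 90-day window opens on day 152 − 90 = 62. Sixteen weekly sessions span 15 × 7 = 105 days. With a first session 0, 7 or 14 days after baseline, the last falls on day 105, 112 or 119, and 7, 8 or 9 sessions lie inside the window. A 7- or 30-day window contains none.

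Assume improvement is linear up to the last session on day L and then held. The share of the final change that a 90-day recall shows is the mean of min(t/L, 1) over days 62 to 152:

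- L = 112: [(112² − 62²)/(2 × 112) + 40]/90 = (38.84 + 40)/90 = 0.876
- L = 152 (sessions stretched to month 5): [(152² − 62²)/(2 × 152)]/90 = 63.36/90 = 0.704

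Apply this to the between-arm d of 0.85 for depression quoted under Intervention Content: 0.85 × 0.876 = 0.74 and 0.85 × 0.704 = 0.60. A two-sample t-test at 80% power and two-sided 5% needs 23 per arm at 0.85, 30 at 0.74 and 45 at 0.60.

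The arithmetic is right, but it does not measure an error, for three reasons:

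- If the later trial uses the same 90-day measure, 0.74 or 0.60 is the effect it will see, and 30 or 45 is the correct size.
- The documents do not give the recall period behind the 0.85, so the discount may be applied twice.
- The calculation holds the SD fixed across recall periods, and step 3 shows how much depends on that.

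**3. How far scoring can move d**

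Assumed model: 40% of participants at zero; the others' rates gamma-distributed with shape 1 and mean 4 per 30 days; month-to-month log-SD 0.5; Poisson counts; mean cut of 40% with a between-person log-SD of 0.8, reached linearly by day 112; everyone kept; d = mean/SD of the paired differences.

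| Scoring | d |
|---|---|
| any/none, 90 days | 0.16 |
| count, 30 days | 0.21 |
| any/none, 30 days | 0.25 |
| count, 90 days | 0.26 |
| square root of 90-day count | 0.39 |
| log(x+1) of 90-day count | 0.42 |

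The spread is 0.42 − 0.16 = 0.26. Over 54 settings (zero share 20, 40 or 60%; mean 2, 4 or 8; shape 0.5, 1 or 2; person log-SD 0.5 or 0.8) the largest-minus-smallest gap runs from 0.14 to 0.51, median 0.25. Without the two any/none codings, which sit poorly with the plan's reference to frequency, the median is 0.19.

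Recall length alone (90- against 30-day count) moves d by a median of 0.06, and the 90-day count gives the larger d in every setting. That is the opposite direction to step 2: for counts, the gain in precision from a longer window more than offsets the treatment weeks inside it. Symptom scores may behave differently, but the equal-SD assumption in step 2 cannot be taken for granted.

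**4. Sampling error at n = 25**

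SE(d) = √(1/25 + d²/50). At d = 0.16 this is 0.201 and at d = 0.42 it is 0.209; over the whole range in step 3 (0.06 to 0.61) it is 0.200 to 0.218. A 95% interval is about ±1.96 × 0.20 = ±0.39.

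**5. The two descriptions of the follow-up visit**

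A weekly schedule ends 152 − 119 = 33 to 152 − 105 = 47 days before month 5, about 5 to 7 weeks. The two descriptions agree if missed weeks are made up; otherwise the word immediately is loose. Every statement of the visit puts it at 5 months, so the data collected are not in doubt.

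**The case for a change.** The best case for acting is that sampling error and an unnamed measure differ in kind. An interval can convey the first; nothing in the plan conveys the second. A reader might guess that the entry subscales are also the depression and anxiety outcomes, but cannot confirm it, and for HIV risk there is nothing to guess from. A four-row table would settle the matter at almost no cost.

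Part of this stands. A reader of this document alone cannot tell which variable lies behind each d, and if several measures per construct are collected, the choice of the main one is open. Naming them would be good documentation.

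What does not stand is the step to an unusable result. The document is a short description of a supplement to a larger grant with a sample of 800. Its silence does not show that the questionnaires were never chosen, and the parent protocol is not available to settle it either way. Recall and scoring are fixed once the baseline form is used, so whoever computes d will know both. That the remedy leaves the data, test and effect size unchanged shows that it records a decision and corrects none. Two further requests, to state that participants at zero stay in and to report untransformed d beside transformed d, answer no fault in the plan: nothing suggests that zeros would be dropped, and the second is a reporting preference.

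**Conclusion.** The observation is accurate, but it describes missing detail that the team must fill in order to run the study at all. No stated rule is shown to give a wrong answer. The comparison of 23 with 30 or 45 per arm should carry no weight: it needs reuse of the entry window, an unchanged SD, and a switch of measure between the pilot and the later trial, none of which the documents state. The count model shows that scoring can move d, typically by about 0.25 across six variants. It rests wholly on assumed rates and curves, and that movement is close to one standard error of d at n = 25. In a one-arm pilot that disclaims significance testing, each d is a rough guide whichever measure is used. This view assumes that the measure will be reported with each d and that a later trial would be planned on the same measure; both are ordinary practice, and nothing in the documents points the other way.
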